### 8.3.4 Validity and Reliability

In the Japanese healthcare system, outcome definitions of CCI [REDACTED] have been validated in the hospital-based setting from different data sources. Previous studies have reported that the positive predictive value (PPV) for CCI [REDACTED] ranged from 78.3% to 93.4% (Ando et al, 2018, Nakai et al, 2021). Moreover, the outcome definitions of CCI [REDACTED] will follow the PMDA's outcome validation reports, which showed that the PPV for CCI [REDACTED] was reported to be 94.22% (95% CI: 89.63-97.19) and the PPV for CCI [REDACTED] was 84.26% (95% CI: 78.96-88.67) (PMDA, 2023b; PMDA, 2023c). Due to the limited resources, a chart review of all the patients in the hospital or a sufficiently large random sample of the hospitalized patients was not possible, so a full set of validity measures such as specificity and NPV are not generally available.

### 8.4 Data Sources

This study is based on the secondary data use of the MID-NET developed by the PMDA. MID-NET is a health information database composed of electronic medical records (EMRs), claims data, and CCI [REDACTED] data from 23 hospitals across ten healthcare organizations. As of December 2022, the database contains data from approximately 6.05 million patients (Yamaguchi et al, 2019), and nearly 1.5 million patients had a record in this network in 2022. The stored data is periodically updated, with updates occurring every week or every 1-3 months depending on the type of data. The available data for analysis includes information on patients' diagnoses, laboratory test results, dosage, and duration of medication administration, as well as details of medical procedures such as surgery dates and types of clinical examinations.

### 8.5 Study Size

The study sample size is expected based on information from the open data of MID-NET. There were 693 romosozumab users, 1,551 PTH analogs users in MID-NET in 2021 (PMDA, 2024b). Assuming 700 romosozumab users per year is accumulated through 5.5 years, the expected number of romosozumab users would be 3,850 by the end of the study. The number of users who would use PTH analogs and oral alendronate are expected to be 8,500 and 60,000, respectively.

Table 4 provides the 95% CI estimates for HR when 1.0 in HR, 3,850 patients in romosozumab, 8,500 patients in PTH analogs and 60,000 patients in oral alendronate, 0.6 or 0.8 years of follow-up period and 0.004 or 0.01 in incidence rates of

cardiovascular outcomes. The incidence rate of cardiovascular outcomes was based on previous literature (Ishikawa et al, 2008).

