Three cohorts will be created mutually and defined based on the prescriptions received for:

- Romosozumab
- PTH analogs: teriparatide, abaloparatide
- Oral alendronate

- Covariates

- Patient and healthcare characteristic
- Fracture risk factors
- Cardiovascular risk factors
- Use of cardioprotective therapies
- Historical use of anti-osteoporosis drugs
- Level of renal insufficiency

- Study Sample Size

Using the MID-NET 2021 open data, we estimated the number of patients who received romosozumab, teriparatide, or oral alendronate over 5.5 years. The expected sample size for this study is: 3,850 patients for romosozumab, 8,500 patients for teriparatide, and 60,000 patients for oral alendronate.

- Data Analysis

- Summary Statistics:

Patient demographic and clinical characteristics will be summarized by cohort of exposure. Discrete variables will be summarized using frequencies and proportions, and continuous variables will be summarized using means and standard deviation (SD) or median and interquartile range (IQR). Incidence rate (number of events divided by person-time of follow-up) of the various outcomes in each exposure cohort will be estimated along with 95% confidence intervals (CI) as a measure of precision.

- Approach to primary objective:

Propensity scores will be calculated for each patient using multiple logistic regression modelling based on baseline demographic characteristics and clinical characteristics. Inverse probability of treatment weights (IPTW) will be created using propensity scores to minimize the measured confounding in the comparison of patients initiating romosozumab relative to patients initiating other specific osteoporosis therapies. Standardized mean differences (SMD) will be used to assess the differences in baseline patient characteristics between the treatment groups. Negative control outcome analyses will be used to detect presence of unmeasured confounding. COX proportional hazards model in the weighted sample will be used to estimate hazard ratio.

- Approach to secondary objective:

The same approach will be performed by the level of renal insufficiency:

1) no chronic renal disease (or eGFR  $\geq 90$  mL/min/1.73 m^2), 2) stage I or II Chronic Kidney Disease (CKD) (or eGFR 60-89 mL/min/1.73 m^2), 3) stage III CKD (or eGFR 30-59 mL/min/1.73 m^2), or 4) stage IV or V (or eGFR  $< 30$  mL/min/1.73 m^2).

- Bias analysis:

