**Table 4. 95% CI estimate for Hazard Ratio 1.0**

CV outcome (IR per one person-year)	Follow-up Time	Estimated 95% CI	
		8,500 patients in PTH analogs	60,000 patients in oral alendronate
0.004	0.6	(0.45, 2.18)	(0.50, 1.91)
	0.8	(0.50, 1.94)	(0.54, 1.75)
0.01	0.6	(0.61, 1.63)	(0.65, 1.52)
	0.8	(0.66, 1.54)	(0.70, 1.45)

Abbreviations used in the table: CI, confidence interval; CV, cardiovascular; IR, incidence rate; PTH, parathyroid hormone receptor.

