#### **8.7.1.2 Primary Analysis**

To describe the study population, we will compute summary statistics for patient demographics and clinical characteristics as of the index date, stratified by the index treatment. Discrete variables will be summarized using frequencies and proportions, and continuous variables will be summarized using means and standard deviation (SD) or medians and interquartile range (IQR), as appropriate. For this study, propensity scores will be estimated and used to create IPTW for each patient in each pairwise treatment comparison. We will then assess the comparability of the weighted cohorts in each comparison, estimate the hazard ratio for each comparison and perform additional analyses to support the result interpretation.

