##### **8.7.2.5.4 Other Sensitivity Analysis**

If the treatment effect varies with the propensity score, different methods will yield different result. Our primary analysis employs IPTW, which aims to balance the distribution of confounding variables between treated and untreated groups while closely approximating the overall study population. Additionally, we will conduct a sensitivity analysis using standard mortality ratio weighting (SMRW) to preserve the results of one of treatment arms (Brookhart M et al., 2013; Stürmer T et al., 2014). Considering the precautionary use of romosozumab as indicated in the labeling, it is possible that some

patients may have unmeasured contraindication for romosozumab. By applying SMRW to make the romosozumab group resemble the comparator group, we can estimate the average treatment effect in the population that was not affected by the warning.

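### Table 4 shows the precision of a crude comparison, while the planned primary hazard ratio is IPTW-weighted; its intervals are close to a best case and should be labelled and restated over a range

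*Protocol*

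**What the plan says.** Protocol Section 8.5 introduces the table in these words: "Table 4 provides the 95% CI estimates for HR when 1.0 in HR, 3,850 patients in romosozumab, 8,500 patients in PTH analogs". The other inputs are a cohort of 60,000 alendronate users, an event rate per person-year of 0.004 or 0.01, and follow-up lasting 0.6 or 0.8 years. The table is headed "Table 4. 95% CI estimate for Hazard Ratio 1.0" and prints one interval per comparator for each of four combinations of rate and follow-up. Neither the section nor the table mentions weighting, overlap of propensity scores or effective sample size.

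The planned analysis is weighted. The Abstract (Section 4) says that a "COX proportional hazards model in the weighted sample will be used to estimate hazard ratio". Section 8.7.1.2 says that "propensity scores will be estimated and used to create IPTW for each patient in each pairwise treatment comparison". Section 8.7.2.4 directs the weights at the overall patient population, and Section 8.7.2.5.4 repeats the aim of "closely approximating the overall study population".

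The Abstract and Section 6.5 warn that precision may be low, but give the low event rate as the only reason. Section 6.6 says that the available sample size will inform how the estimate is interpreted.

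**The concern.** A reader will take Table 4 as the expected precision of the primary result, because nothing marks it otherwise. If its intervals belong to an unweighted comparison, they describe a different estimator from the one that will be reported.

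The gap falls on the arm that decides precision. Romosozumab is the smaller arm in both contrasts: 3,850 of 63,850 patients (6%) against alendronate and 3,850 of 12,350 (31%) against PTH analogs. Weights that target the overall population vary most among patients in the smaller arm. The 60,000 alendronate patients make that column look the more precise one, but they cannot make up for information lost among 9 to 31 romosozumab events.

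In a safety study, what matters is how large an excess risk the upper limit could rule out. That is what an optimistic table misstates.

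**Working it through.** **Inputs.** From Section 8.5: N = 3,850 (romosozumab), 8,500 (PTH analogs), 60,000 (alendronate); rate 0.004 or 0.01 per person-year in both arms; follow-up 0.6 or 0.8 years; hazard ratio 1.0. z = 1.96.

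**Step 1: reproduce Table 4.** Expected events are d = N × rate × follow-up, rounded to whole numbers. With d1 for romosozumab and d0 for the comparator,

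RR = (d1/3,850) / (d0/N), limits = RR × exp(±1.96 × √(1/d1 + 1/d0)).

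| Comparator | Rate | Years | d1 / d0 | RR | Computed | Printed |
|---|---|---|---|---|---|---|
| PTH analogs | 0.004 | 0.6 | 9 / 20 | 0.994 | 0.452, 2.182 | 0.45, 2.18 |
| PTH analogs | 0.004 | 0.8 | 12 / 27 | 0.981 | 0.497, 1.937 | 0.50, 1.94 |
| PTH analogs | 0.01 | 0.6 | 23 / 51 | 0.996 | 0.609, 1.629 | 0.61, 1.63 |
| PTH analogs | 0.01 | 0.8 | 31 / 68 | 1.007 | 0.658, 1.539 | 0.66, 1.54 |
| Alendronate | 0.004 | 0.6 | 9 / 144 | 0.974 | 0.497, 1.910 | 0.50, 1.91 |
| Alendronate | 0.004 | 0.8 | 12 / 192 | 0.974 | 0.544, 1.745 | 0.54, 1.75 |
| Alendronate | 0.01 | 0.6 | 23 / 360 | 0.996 | 0.653, 1.518 | 0.65, 1.52 |
| Alendronate | 0.01 | 0.8 | 31 / 480 | 1.007 | 0.700, 1.447 | 0.70, 1.45 |

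All 16 limits agree to two decimals. Rounding is needed for the exact match: with unrounded events and a ratio of exactly 1.0, the log-widths still agree within about 2%, but single limits differ (0.56 against the printed 0.54 at worst). The table therefore holds a crude interval with a variance inflation of exactly 1.

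**Step 2: where the variance sits.** Romosozumab's share is (1/d1)/(1/d1 + 1/d0). For alendronate with 9 and 144 events it is 0.1111/(0.1111 + 0.0069) = 94%. For PTH analogs with 9 and 20 events it is 0.1111/(0.1111 + 0.0500) = 69%. The other rows give the same shares to within a percentage point.

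**Step 3: how much weighting might inflate it.** The protocol gives no propensity-score distribution, so this step is an assumption. Take a linear predictor that is normal within each arm, with separation √2 × probit(c) for c-statistic c, weights 1/PS for romosozumab, and Kish inflation D1 = E[w²]/E[w]².

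| c-statistic | 0.58 | 0.60 | 0.65 | 0.70 | 0.75 |
|---|---|---|---|---|---|
| D1 against alendronate | 1.08 | 1.12 | 1.3 | 1.65 | 2.3 |
| D1 against PTH analogs | 1.04 | 1.07 | 1.16 | 1.35 | 1.70 |

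**Step 4: effect on the intervals.** Keep Table 4's own method, including its rounded counts and centring, and inflate only the romosozumab term: limits = RR × exp(±1.96 × √(D1/d1 + 1/d0)).

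| Alendronate row | Printed | D1 = 1.25 | D1 = 1.5 | D1 = 2 |
|---|---|---|---|---|
| 0.004, 0.6 years | 0.50, 1.91 | 0.46, 2.06 | 0.43, 2.20 | 0.38, 2.49 |
| 0.01, 0.8 years | 0.70, 1.45 | 0.67, 1.51 | 0.65, 1.56 | 0.61, 1.67 |

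Worked example, top row with D1 = 1.5: √(1.5/9 + 1/144) = 0.417; 0.974 × exp(±1.96 × 0.417) = (0.43, 2.20).

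**The case against.** The strongest reply is that Table 4 is a correct calculation from declared inputs. It never claims to be weighted, and the database was not accessible when the protocol was written, so no propensity distribution was available. The low-precision caveats already temper it, Section 8.7.2.4 already avoids covariates that would cost precision without reducing bias, and the final report will carry the actual weighted interval. Effective sample size and weight handling commonly belong in the SAP.

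Much of this stands. The table's arithmetic is right for a crude comparison. Widening is small if the cohorts are alike. The Kish factor is an approximation that treats weights as unrelated to outcome, and adjusting for outcome predictors could recover some precision; wider is the expected direction, not a certainty. The practical consequence is also bounded: the trial contrast cited in Section 6.3 (2.5% against 1.9%, a ratio of about 1.32) lies inside every printed interval, so widening reverses no exclusion of that effect.

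It does not remove the mismatch. The caveats name only the event rate, and nothing in Section 8.5 tells the reader that the intervals are unweighted.

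Three stronger readings are tempting but unsupported:

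- **That the protocol expects strong channelling.** The Abstract speaks only of potential channelling bias, and Section 8.7.2.1 assumes that confounding exists without giving its strength. The contraindication raised in Section 8.7.2.5.4 is unmeasured, so it cannot enter the propensity score. The renal warning in Section 8.7.1.3 is shared by romosozumab and alendronate.
- **That the study loses power.** It is an estimation study, and the checklist in Appendix B marks hypotheses as not applicable.
- **That an average romosozumab weight near 17 (63,850/3,850) is itself the problem.** Only the relative spread of the weights costs precision.

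**Conclusion.** The point holds as a mismatch between the precision statement and the planned estimator. It is not an arithmetic error, and it invalidates no test. That Table 4 is crude is established by the match on all 16 limits; that the primary hazard ratio is weighted to the overall population is stated in four places.

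The table is therefore close to a best case and is expected to overstate precision, mainly through the romosozumab arm. The size cannot be fixed from the protocol. Under the logit-normal assumption, the romosozumab variance rises by 4% to 8% at c = 0.58, and by 70% (PTH analogs) to 130% (alendronate) at c = 0.75. In the least informative alendronate row, the upper limit of 1.91 would move to between 2.06 and 2.49 for inflation of 1.25 to 2; in the most informative row, 1.45 would move to between 1.51 and 1.67. Because Table 4 is the only numerical precision statement, the correction is worth making.

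**What to change.** 1. Label the present Table 4 *unweighted, best case*, and say in Section 8.5 that the weighted interval is expected to be wider.
2. Add rows using variance D1/d1 + D2/d2, with D1 and D2 the inflation in the romosozumab and comparator arms, over a stated range of D1 that includes small values, for example 1.1, 1.25, 1.5 and 2.
3. Once propensity scores are fitted and before outcomes are examined, compute the effective sample size per arm, restate the expected interval for each contrast, and use that figure when interpreting the result under Section 6.6. The details can sit in the SAP.

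The cost is one recalculated table and a sentence or two in Section 8.5. No new data are needed. The stated precision becomes less favourable.

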**Table 4. 95% CI estimate for Hazard Ratio 1.0**

CV outcome (IR per one person-year)	Follow-up Time	Estimated 95% CI	
		8,500 patients in PTH analogs	60,000 patients in oral alendronate
0.004	0.6	(0.45, 2.18)	(0.50, 1.91)
	0.8	(0.50, 1.94)	(0.54, 1.75)
0.01	0.6	(0.61, 1.63)	(0.65, 1.52)
	0.8	(0.66, 1.54)	(0.70, 1.45)

Abbreviations used in the table: CI, confidence interval; CV, cardiovascular; IR, incidence rate; PTH, parathyroid hormone receptor.

## 8.6 Data Management

Amgen will take responsibility for application for the study permits, obtaining necessary approvals, and access to the study data. The data will be stored and analyzed in accordance with the MID-NET Utilization Guidelines (PMDA, 2024c).

### 8.6.1 Obtaining Data Files

Trained and registered MID-NET users can centrally extract MID-NET data using the extraction script from the on-site center. They can access the analysis dataset and the statistical information generated from it within the MID-NET data center, either from the on-site center or from a remote MID-NET environment. The remote connection requires IT security management.

The planned criteria of the patients to be extracted from MID-NET is listed as follows:

- Patients who used any of the study medications (romosozumab, PTH analogs, or oral alendronate) after 4 March 2019.

### 8.6.2 Linking Data Files

All patient-level data contained in the MID-NET database will be extracted by the criteria in Section 8.6.1 and linked by the unique identifier provided in the data system.

### 8.6.3 Review and Verification of Data Quality

The general principles and procedures for reviewing and verifying data quality will be described in detail in the SAP. All data checks to be performed on completeness, plausibility and consistency of collected data will be described in detail with identification of data discrepancies. The reliability of the data in MID-NET is ensured by PMDA from

the following points: data reliability, reliability of data standardization, reliability of data extraction, reliability of data transmission to the data center and reliability of conversion to SAS data (Nakashima et al, 2018).

## **8.7 Data Analysis**

### **8.7.1 Planned Analyses**

#### **8.7.1.1 Feasibility Analyses**

A detailed feasibility step will be applied in order to define and operationalize the key design elements in the MID-NET database. Considering the data relevance and reliability, we will assess the availability of laboratory information (eg, serum creatine or eGFR), date of administration, day supply of the prescriptions, and relevant diagnosis to test the validity of coding algorithms.

#### **8.7.1.2 Primary Analysis**

To describe the study population, we will compute summary statistics for patient demographics and clinical characteristics as of the index date, stratified by the index treatment. Discrete variables will be summarized using frequencies and proportions, and continuous variables will be summarized using means and standard deviation (SD) or medians and interquartile range (IQR), as appropriate. For this study, propensity scores will be estimated and used to create IPTW for each patient in each pairwise treatment comparison. We will then assess the comparability of the weighted cohorts in each comparison, estimate the hazard ratio for each comparison and perform additional analyses to support the result interpretation.

#### **8.7.1.3 Secondary Analysis**

For secondary objective, we will use the same method that we used in primary analysis and restrict to a subset that have available information on renal insufficiency. Since romosozumab and oral alendronate have a warning for use in patients with creatinine clearance less than 30 mL/min/1.73 m^2, patients treated with these therapies may exhibit a lower prevalence of renal insufficiency compared to those treated with PTH analogs. To ensure the comparability between treatment groups, we will limit the analyses to patients with similar levels of renal function to mitigate potential bias. The subgroup analyses will be performed based on the following criteria: 1) no chronic renal disease (or eGFR  $\geq$  90 mL/min/1.73 m^2), 2) stage 1 or II CKD (or eGFR 60-89 mL/min/1.73 m^2), 3) stage III CKD (or eGFR 30-59 mL/min/1.73 m^2), or 4) stage IV or V (or eGFR < 30 mL/min/1.73 m^2).

## **8.7.2 Planned Method of Analysis**

### **8.7.2.1 General Considerations**

Given that MID-NET database is not accessible for now, descriptive analysis will be conducted prior to propensity score weighting portion of this study. To describe the incidence rate for outcomes, by romosozumab therapy, by PTH analogs, and by oral alendronate, the number of patients with events will be divided by person-time of follow-up. Incidence rate as well as hazard ratio will be accompanied by the corresponding 95% confidence intervals (CI) as a measure of precision.

We assume that measured and unmeasured confounding exist, and plan to perform a set of analyses to assess the comparability between treatment groups. Standardized mean differences (SMD) will be used to assess how different the baseline characteristics are between the treatment groups before and after propensity score weights are applied. We will consider the measured confounders with SMD values less than 0.1 as having negligible differences (Austin, 2009). In addition, negative control outcome analyses will be performed to rule out any potential unmeasured confounders (McGrath et al., 2020). For each negative control outcomes, risk difference and risk ratio in negative control outcomes will be calculated. The comparability of treatment groups will be explored by examining overall trends in effect estimates and the precision of CI across all negative control outcomes within an exposure contrast. We will assume there is significant uncontrolled confounding if the measure of association is not likely to be null.

### **8.7.2.2 Missing or Incomplete Data and Lost to Follow-up**

There will be no imputation of missing data in this study. A proportion of patients has laboratory information in the data source. Given that MID-NET is hospital-based data network and does not include information from other resources, this study will use extra data sources to describe how complete the capture for the endpoints is in a closed healthcare system within therapy cohorts. This way, we might be able to assess the possible size and effect of incomplete capture/ misclassification of endpoints between treatment groups on planned main analysis.

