**Table 3. List of covariates**

Characteristic	MID-NET	Note/ Covariate assessment period
Age, mean (SD)	Yes	On index date
Race/ethnicity	No	Most of all is Japanese
Sex (Male, female)	Yes	On index date
Year of cohort entry	Yes	On index date
Lifestyle risk factors		The closest measurement taken within one year before the index date, including the index date itself.
Smoking index	Yes	This information might be only recorded when patients are admitted to the hospital.
Information of lab value		The closest measurement taken within one year before the index date, including the index date itself.
Height, cm, mean (SD)	Yes	
Weight, kg, mean (SD)	Yes	
Body mass index, mean (SD)	Yes	Calculated with height and weight, kg/m 
Serum creatinine, mg/dL, mean (SD)	Yes	
eGFR, mL/min/1.73 m 	Yes	% among three cohorts to be confirmed
Level of renal insufficiency a		Calculated with serum creatine level. Classified into four groups. >= 90 (Normal); 60 -< 90 (Mild); 30 -< 60 (Moderate); < 30 (Severe)
Fasting plasma glucose, mg/dL, Mean (SD)	Yes	
HbA1c, %, Mean (SD)	Yes	
HDL-C, mg/dL, Mean (SD)	Yes	
LDL-C, mg/dL, Mean (SD)	Yes	
Triglyceride level, mg/dL, Mean (SD)	Yes	
History of healthcare utilization		Within one year prior to index
Number of inpatient hospitalizations	Yes	
Number of outpatient visits	Yes	
Number of cardiovascular-related hospital days	Yes	
Number of serum creatinine tests	Yes	% among three cohorts to be confirmed
Number of lipid-related lab tests	Yes	% among three cohorts to be confirmed
History of fracture	Yes	All available history unless otherwise specified
Any fracture	Yes	
Vertebral fractures	Yes	
Hip fracture	Yes	

Characteristic	MID-NET	Note/ Covariate assessment period
History of fracture hospitalizations	Yes	
Osteoporosis diagnosis	Yes	
History of use of anti-osteoporosis drugs		All available history unless otherwise specified
Oral bisphosphonates	Yes	
IV bisphosphonates	Yes	
Anti-RANKL antibody (Denosumab)	Yes	
PTH analogs (Teriparatide or abaloparatide)	Yes	
Selective estrogen receptor modulators (Raloxifene, bazedoxifene)	Yes	
Estrogen replacement therapy	Yes	
Historical use of the medication that increased fracture or osteoporosis risk	Yes	Fracture/OP risk factors, Within one year prior to index
Anticonvulsant		
Antidepressant	Yes	
Antiparkinsonian	Yes	
Antipsychotic	Yes	
Benzodiazepine	Yes	
NSAIDs and COX-2 inhibitor	Yes	

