### 8.7.2.4 Analysis of the Primary, Secondary, and CCI

Primary endpoint is consistent with primary objective.

- Composite endpoint of hospitalized AMI, cerebral hemorrhage and cerebral infarction

Secondary endpoint is consistent with secondary objective.

- Composite endpoint of hospitalized AMI, cerebral hemorrhage and cerebral infarction

CCI

We will use two methods to estimate the incidence of each endpoint. First, we will calculate simple incidence rates (total number of patients with at least one event in the cohort divided by the sum of person-time to the first censoring event in the cohort) multiplied by 100 for each outcome and cohort. These rates do not account for treatment selection. Second, we will estimate propensity scores for each patient in the cohort using multivariable logistic regression with baseline covariates related to patient and clinical characteristics (see Section 8.3.3). The propensity score balances the distribution of observed covariates between treatment groups. We will include covariates that are either true confounders (to reduce bias) or related to the outcome (to increase precision). We will avoid covariates that are only related to the exposure but weakly related to the outcome, as they may decrease precision without reducing bias much (Brookhart et al, 2006). We will use inverse probability of treatment weights (IPTW) to estimate the rates of each outcome by time t in the overall patient population.

Specifically,  $F(T(a) < t)$  will be estimated with:

$$F(T(a) < t) = \frac{1}{n} \sum_{i=1}^n \frac{I(T_i < t) I(A_i = a) \Delta_i}{\Pr(\Delta_i = 1 | A_i, W_i)}$$

where  $A_i$  is an indicator of the observed treatment assignment,  $T(a)$  is the time of the (possibly counterfactual) outcome that would be observed if the patient were treated with  $A_i=a$ , and  $\Delta_i$  is an indicator that the patient was uncensored.

The propensity score model,  $\Pr(A_i=a|W_i)$ , will be estimated using logistic regression, and will contain a rich set of baseline covariates detailed in Section 8.3.3. We will estimate the hazard ratio and 95% confidence interval bands at 12 months by using COX proportional hazards model. Patients will be censored if any of the following happen: they discontinue the study medication (or switch to a different medication), one year from the start of study medication (index date), end of available data in the database, or death, whichever is earliest.

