##### **8.9.1.1 Measurement Error(s)/Misclassification(s)**

MID-NET is an open healthcare system that may result not capture all the relevant data on exposure, outcome and covariates for the study. Since romosozumab appears to have more complete data related to other specific therapies in the MID-NET system, we will evaluate it with an external database that is a closed healthcare system. This will help us assess if there is any differential bias between the treatment groups. Moreover, the information on social behavior such as smoking because the history of smoking is only available in inpatient claims. Since alcohol consumption and risk of fall could not be directly measured from the diagnoses, these variables were not included in this study.

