### **8.9.1.3 Selection Bias**

Given that the follow-up period of this study is relatively short, the likelihood of participants being lost to follow-up may be low. However, if we observe that the censoring varies between treatment groups, we cannot completely eliminate the risk of selection bias. Additionally, the availability of the laboratory information may be affected by patient characteristics and medical practice (Komamine et al., 2021). The potential selection bias cannot be avoided completely.

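### The ban on imputation, with partly recorded covariates in the propensity model, leaves no stated way to give every patient a weight in the primary analysis

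*Protocol*

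**What the plan says.** Protocol Section 8.7.2.2 sets a rule without exceptions: "There will be no imputation of missing data in this study". It then concedes that "A proportion of patients has laboratory information in the data source".

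Section 8.7.2.4 says the propensity model "will be estimated using logistic regression, and will contain a rich set of baseline covariates detailed in Section 8.3.3". Table 3 in that section lists height, weight, body mass index, serum creatinine, eGFR, fasting glucose, HbA1c, HDL-C, LDL-C, triglycerides and a smoking index. For these the assessment rule is "The closest measurement taken within one year before the index date, including the index date itself". On smoking, Table 3 notes "This information might be only recorded when patients are admitted to the hospital", and Section 8.9.1.1 is firmer: "the history of smoking is only available in inpatient claims".

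The Abstract and Section 8.7.2.4 promise a propensity score for every patient. Sections 8.7.2.4 and 8.7.2.5.4 present the weighted analysis as describing the whole study population. Section 8.7.1.3 limits only the secondary analysis to patients with renal information. Section 8.9.1.3 accepts that "the availability of the laboratory information may be affected by patient characteristics and medical practice".

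**The concern.** A logistic regression cannot score a patient who lacks a value for one of its covariates. With imputation ruled out and no other device named, standard practice drops that patient from the propensity model, and so from the weighted Cox model.

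Two things are at stake. The first is the population. The primary hazard ratio would describe patients who happened to be tested and, if smoking is required, those with smoking recorded at an admission in the year up to the index date. Testing and admission may differ between drugs. The second is precision. Table 4 is computed on full cohorts, in a study that already expects wide intervals.

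**Working it through.** **1. The statements side by side.**
- Imputation: barred for the whole study (8.7.2.2).
- Partly observed covariates: listed in Table 3 and fed to the propensity model (8.7.2.4).
- Coverage: every patient scored, whole population represented (Abstract, 8.7.2.4, 8.7.2.5.4).
- Restriction to patients with renal data: secondary analysis only (8.7.1.3). This implies that the primary analysis keeps patients without such data, although eGFR is itself a Table 3 covariate.

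These cannot all hold unless a patient with a missing value can still be scored. Nothing else in the protocol supplies the means:
- Sections 8.3.3 and 8.9.3 drop covariates for low prevalence, not for missingness.
- The feasibility step (8.7.1.1) checks laboratory availability but carries no decision rule and does not mention smoking or body mass index.
- The external closed database (8.7.2.2, 8.9.4) helps to judge incomplete capture but cannot supply a MID-NET patient's missing value.
- The attrition table (8.7.2.3.1) follows eligibility criteria only, so losses at the propensity step would not appear in it.

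**2. Reproducing Table 4.** Inputs from Section 8.5: 3,850 romosozumab, 8,500 PTH analog and 60,000 alendronate patients; rates 0.004 or 0.01 per person-year; follow-up 0.6 or 0.8 years. Expected events are e = N × rate × follow-up. The interval at a hazard ratio of 1 is exp(±1.96 × √(1/e1 + 1/e0)).

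For rate 0.004 and 0.6 years against PTH analogs:
- e1 = 3,850 × 0.004 × 0.6 = 9.24
- e0 = 8,500 × 0.004 × 0.6 = 20.4
- standard error = √(1/9.24 + 1/20.4) = 0.397
- interval (0.46, 2.18); Table 4 gives (0.45, 2.18)

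Across all eight cells the upper limits agree within 2% and the lower limits within about 0.02. Table 4 therefore makes no allowance for patients lost to missing covariates.

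**3. The completeness figures available.** Section 6.5 gives creatinine testing only:
- romosozumab 1,908/1,989 = 95.9%
- alendronate 18,570/19,118 = 97.1%
- PTH analogs 2,978/3,156 = 94.4%

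These refer to testing at any time in 2021-2023, not in the year before the index date, and to one item.

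**4. Effect of a complete-case fraction f.** The value of f is not in the protocol, so this is a range of assumptions, applied equally to all cohorts. Rate 0.004, 0.6 years:

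| f | Romosozumab events | vs PTH analogs | vs alendronate |
|---|---|---|---|
| 1.00 | 9.2 | (0.46, 2.18) | (0.51, 1.94) |
| 0.95 | 8.8 | (0.45, 2.22) | (0.51, 1.98) |
| 0.90 | 8.3 | (0.44, 2.27) | (0.50, 2.02) |
| 0.70 | 6.5 | (0.39, 2.53) | (0.45, 2.21) |
| 0.60 | 5.5 | (0.37, 2.73) | (0.42, 2.36) |
| 0.50 | 4.6 | (0.33, 3.00) | (0.39, 2.56) |

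For f = 0.60 against PTH analogs: e1 = 5.54, e0 = 12.24, standard error √(1/5.54 + 1/12.24) = 0.512, and exp(1.96 × 0.512) = 2.73. The alendronate row uses e0 = 86.4.

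At the creatinine level (f about 0.95) the change is negligible. A material loss needs low joint completeness of lipids, glucose, HbA1c, body mass index and smoking. If smoking were required, f could not exceed the share of patients with smoking recorded at an admission in the year up to the index date, which is also not given.

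**The case against.** The best defence is that the protocol never prescribes a complete-case analysis. Deleting incomplete records is what software does by default, not a written rule. A 'not measured' category, or leaving a sparse item out, is compatible with a ban on imputation. The promise to score every patient, and the renal restriction confined to the secondary analysis, suggest that the authors meant to keep everyone.

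Table 3 is also a candidate list rather than a fixed model. Section 8.7.2.4 applies selection criteria, some items overlap (height, weight and body mass index; creatinine and eGFR), and Section 8.9.3 leaves model building to the SAP. Coded diagnoses and drugs for diabetes, lipid disorders, obesity and kidney disease cover some of the same ground. Section 8.9.1.3 discloses selection by laboratory availability, and item 10.7 of the ENCePP checklist openly answers that missing-data methods are not described.

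Most of this stands, and it limits the point. A reader might infer that the plan deletes every patient with any unmeasured value and leaves a small, unusually sick cohort. The documents do not support that. No deletion rule is stated, no joint completeness or prior-admission rate is given, and the only completeness figures exceed 90%. That the retained patients would be sicker is a guess from how smoking is captured; Section 8.9.1.3 says only that laboratory availability may depend on patient characteristics and practice.

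What the defence does not answer is that the ban itself is a fixed protocol rule, not a detail left open. As worded, it prevents the SAP from using multiple imputation even as a sensitivity analysis. Intending to keep everyone does not say how. Disclosing the selection does not reduce it.

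**Conclusion.** The point holds in limited form. The protocol bars all imputation, puts partly recorded covariates into a logistic propensity model, and names no means of keeping patients with missing values. As written, neither the stated primary population nor the Table 4 precision is secured, and the secondary-only renal restriction does not fit a primary analysis that drops incomplete records by default.

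The size of the loss is unknown. It could be trivial, as with creatinine alone, or material: under the 60% assumption the upper limit against PTH analogs rises from 2.18 to about 2.73. These figures assume equal completeness across cohorts and unweighted event counts. They show loss of precision only; the direction and size of any selection bias cannot be derived from the protocol.

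This should be fixed before the SAP is final. It does not undermine the design.

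**What to change.** In Section 8.7.2.2, confine the ban on imputation to exposure and outcome. Then state that:
- every eligible patient receives a weight in the primary analysis;
- partly observed covariates enter the propensity model as categories that include a 'not measured' level, or are left out if too sparse, relying on the coded diagnoses and drugs already in Table 3;
- multiple imputation and complete-case results are reported as sensitivity analyses;
- completeness of each such covariate, and of all jointly, is reported by treatment cohort.

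The cost is a change of wording and modest programming. The method has one real assumption: a 'not measured' level adjusts properly only if treatment choice depended on the recorded value, or on the fact that none was recorded, and not on the unseen value. The two sensitivity analyses show how far the result leans on that assumption.
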